3.3.4 Other Data to Be Characterized and Reported

- Rate of occurrence of all adverse events
- Utilization of continuous renal replacement therapy (CRRT), ultrafiltration and dialysis
- Change in serum creatinine
- Change in eGFR
- Change in diuretic doses
- Change in urine sodium excretion
- Changes in cardiac output and cardiac power output^{vi}
- QoL changes from KCCQ and EQ5D
- Change in dyspnea assessment
- Changes in echo parameters (includes CO)
- Rates of hemolysis as measured by Lactate Dehydrogenase (LDH), Plasma Free Hb (pFH) and urine hemoglobin

^{vi} Cardiac Output (CO) and Cardiac Power Output (CPO) will be calculated by the sponsor. CPO parameters to be collected: SaO₂ (as measured by pulse oximeter), SvO₂ (as measured on mixed venous gas from PA catheter), hemoglobin (from CBC), weight, height, blood pressure [to calculate mean arterial pressure (MAP)], and heart rate.

3.4 Study Population

This study will enroll up to 60 patients in order to treat 30 patients using Aortix with ADHF (irrespective of ejection fraction) refractory to medical management with persistent clinical signs of congestion and worsening renal function.

3.4.1 Inclusion Criteria

The patient must meet **ALL** of the following criteria:

- 1) Admitted to the hospital with a primary diagnosis of acute decompensated heart failure, either heart failure with reduced or preserved ejection fraction (HFrEF, HFpEF or HFmEF);
- 2) Worsening renal function (serum creatinine increase by ≥ 0.3 mg/dl [≥ 27 μ mol/L]) despite 48 hours of intravenous diuretic therapy. Increase can be compared to a baseline value taken within 90 days of hospitalization or during hospitalization;
- 3) Objective measure of congestion (Elevated PCWP [≥ 20 mmHg] OR Elevated CVP [≥ 12 mmHg]) obtained via catheter measurement;^{vii}
- 4) Persistent clinical signs and/or symptoms of congestion despite diuretic therapy (one or more of the following):
 - a) dyspnea at rest or with minimal exertion,
 - b) paroxysmal nocturnal dyspnea,
 - c) orthopnea,
 - d) lower extremity edema ($\geq 2+$),
 - e) elevated jugular venous pressure,
 - f) pulmonary rales,
 - g) enlarged liver or ascites,
 - h) pulmonary vascular congestion on chest x-ray;
- 5) Age >21 years and able to provide written informed consent.

^{vii} This assessment requires patient to sign informed consent.

3.4.2 Exclusion Criteria

- 1) Treatment with high dose IV inotropes within the last 48 hours. High dose is defined as > 1 unit of inotrope (excluding digoxin) as follows:
5 µg/kg/min dopamine = 1 unit,
5 µg/kg/min dobutamine = 1 unit,
0.375 µg/kg/min milrinone = 1 unit,
(for example, dopamine 2.5 µg/kg/min + dobutamine 2.5 µg/kg/min = 1 unit; dobutamine 2.5 µg/kg/min + milrinone 0.1875 µg/kg/min = 1 unit);
- 2) Treatment with vasopressors to maintain blood pressure as per exclusion #3;
- 3) Active and ongoing hypotension defined as a systolic blood pressure < 90 mmHg lasting more than 30 minutes or a mean arterial pressure (MAP) < 60 mmHg lasting more than 30 minutes;
- 4) Acute Kidney Failure defined as increase in serum creatinine to ≥ 4.0 mg/dL (≥ 353.6 µmol/L) within the last 48 hours;
- 5) Exposure to intravenous contrast, aminoglycosides or high dose NSAIDs in the 48 hours before enrollment;
- 6) Known or suspected contrast induced nephropathy;
- 7) Prior kidney transplant, isolated single kidney, stage V Chronic Kidney Disease (eGFR ≤ 15) at admission OR use of dialysis, continuous renal replacement therapy (CRRT) or aquapheresis (ultrafiltration) in last 90 days;
- 8) Urologic intervention (except indwelling urinary (Foley) catheter)) within the last 7 days;
- 9) Known cirrhosis or shock liver;
- 10) Presence of an active infection;
- 11) Prior heart transplant in the last 2 years, heart failure due to rejection of a previous heart transplant, planned heart transplantation before the 30-day follow-up visit;
- 12) Current or previous support with a durable LVAD at any time or use of an intra-aortic balloon pump, extracorporeal membrane oxygenation (ECMO), or percutaneous ventricular assist devices (e.g. Impella or TandemHeart) currently or within the last 30 days;
- 13) Patient has known hypo- or hyper coagulable state such as disseminated intravascular coagulation or heparin induced thrombocytopenia (HIT);
- 14) Known cardiac amyloidosis;
- 15) Acute myocardial infarction Type 1 within 30 days of enrollment, or planned coronary revascularization;
- 16) Stroke within 30 days of enrollment;
- 17) Severe Bleeding Risk (any of the following):
 - a) Previous intracranial bleed unless there is documentation in the medical record (from a physician that is not part of the study) that the patient can safely use anticoagulation for 7 days,
 - b) GI bleeding within 6 months requiring hospitalization and/or transfusion,
 - c) Recent major surgery within 6 months if the surgical wound is judged to be associated with an increased risk of bleeding,

- d) Endovascular procedure with ilio-femoral access > 6 FR within 30 days,
 - e) Platelet count <75,000 cells/mm³,^{viii}
 - f) Uncorrectable bleeding diathesis or coagulopathy (e.g. INR ≥2 not due to anticoagulation therapy);
- 18) Current endovascular stent graft in the descending aorta or any femoro-iliac vessels;
- 19) Contraindicated Anatomy:^{ix}
- a) Descending aortic anatomy that would prevent safe placement of the device [<18mm or >31mm aorta diameter at deployment location (measured between the superior aspect of the T10 vertebra and superior aspect of the L1 vertebra)],
 - b) Ilio-femoral diameter or peripheral vascular anatomy that would preclude safe placement of a 21F (outer diameter) introducer sheath,
 - c) Abnormalities or severe vascular disease that would preclude safe access and device delivery (e.g. aneurysm with thrombus, marked tortuosity, significant narrowing or inadequate size of the abdominal aorta, iliac or femoral arteries, or severe calcification),
 - d) Known connective tissue disorder (e.g. Marfan Syndrome) or other aortopathy at risk of vascular injury;
- 20) Known hypersensitivity or contraindication to study or procedure medications (e.g. anticoagulation therapy) or device materials (e.g. history of severe reaction to nickel or nitinol);
- 21) Positive pregnancy test if of childbearing potential;
- 22) Participation in any other clinical investigation that is likely to confound study results or affect the study;
- 23) Unable or unwilling to undergo screening (imaging, PA Catheter placement), device implant and retrieval procedures.

3.5 Study Duration

It is expected that study patients will be enrolled over a period of approximately 12-24 months within Australia and the USA. The total duration of a patient's participation in the study is approximately 1.5 months including screening, enrollment, therapy and follow-up.

3.6 Subject Withdrawal and Discontinuation

Every effort shall be made to keep all patients in the study for the duration. However, the patient's participation in this study is completely voluntary. If the patient decides not to participate or to withdraw from the study, their decision will have no effect on any services or treatment the patient is currently receiving and will not affect their relationship with their doctor. Additionally, the Principal Investigator may withdraw or choose not to enroll a patient if they feel they do not meet the protocol defined criteria or if it is in the best medical interest of the

^{viii} If patient doesn't have a, b, c, d or f, but the platelet count at time of enrollment is <75,000 cells/mm³, patient can be enrolled and the platelet count re-assessed at the time of the procedure. The platelet count at time of procedure should be ≥75,000 cells/mm³. If platelet count at time of procedure is <75,000 cells/mm³, patient would be a screen failure.

^{ix} Anatomy assessment requires patient to sign informed consent.

patient in question. A patient may also be withdrawn if they have a terminal event, defined as a heart or kidney transplant, death, dialysis, ultrafiltration or CRRT or LVAD implant.

In cases of voluntary patient withdrawal, all data collected from the time of informed consent to the time of voluntary withdrawal may be used. If a patient chooses to withdraw from the study prematurely, the reason for withdrawal will be documented on the applicable electronic case report form (eCRF). If patient requests to withdraw after the investigational Aortix Pump is deployed, the Aortix Pump must be retrieved, and the patient shall be instructed and encouraged to continue follow-up visits for evaluation of the patient's health status.

A patient who considers withdrawing from the study must be informed by the Investigator about modified follow-up options (e.g., telephone contact, a contact with a relative or treating physician, or information from medical records). If the patient withdraws consent for disclosure of future information, the Sponsor may retain and continue to use any data collected before such a withdrawal of consent. Procyrion or its delegate will request Investigators to collect information on patients' vital status (dead or alive; date of death when applicable) at study closure from publicly available sources, in accordance with local regulations. Knowledge of the vital status at study closure in all patients is crucial for the integrity of the study.

In the event the patient withdraws consent during the study, the date of withdrawal will be documented. If the investigator voluntarily removes a patient from further study participation, supporting documentation must be in place for the rationale and date of removal. Every attempt will be made to contact patients who are noncompliant to the follow-up requirement. Patients will be considered lost to follow-up once the following steps have been taken:

[figure not shown]
- At least three (3) phone calls should be made to the patient. Each attempt should be clearly documented in the source documents and the response or lack thereof should be captured. Additionally, sites should send a certified letter to the most recent known address if unable to reach the patient by phone.
- Contact the patient's family doctor (if known) to obtain survival status and information on adverse events (if any).
- If there is no response, the patient will be considered lost to follow-up. The sponsor should be notified, and the Study Exit form should be completed.

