3.3 Study Endpoints

3.3.1 Primary Safety Endpoints

- 1 Rate of Occurrence of Serious Adverse Events (rate will be calculated and reported) [timeframe: enrollment to 30 day visit]
- 2 Rate of Occurrence of Serious Procedure Related Adverse Events (rate will be calculated and reported) [timeframe: procedure to 30 day visit]

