4.8 Follow-Up

Patients with the pump implanted will be followed for adverse events for 30 days (± 7 days) post device retrieval. If implanted patients are still hospitalized at 30 days due to an adverse event relating to the device or any study related procedures, they must be followed until resolution of the adverse event, resolution with sequelae, or until a terminal event. Protocol required data collection for patients with the pump implanted will be for 30 days post device retrieval (± 7 days) per **Appendix A**.

The following data will be collected:

- NYHA classification
- Cardiovascular exam (edema, pulmonary auscultation, weight),
- Vital signs (HR, BP, RR)
- Dyspnea evaluation
- KCCQ, EQ5D
- Document current cardiovascular/renal medications and adverse events
- Blood and urine labs per **Appendix A**

Patients that have an attempted implant but do not have the pump implanted will be followed for adverse events for 30 days (± 7 days) post attempted implant. If attempted implant patients are still hospitalized at 30 days due to an adverse event relating to the device or any study related procedures, they must be followed until resolution of the adverse event, resolution with sequelae, or until a terminal event.

Terminal events are death, LVAD implantation, heart and/or kidney transplantation, dialysis, ultrafiltration or CRRT.

Patients who are enrolled and undergo anatomy screening and/or invasive hemodynamic measurements who do not have an attempted implant will be followed for adverse events for 7 days (\pm 2 days) post anatomic screening or invasive hemodynamics (whichever is later) or until hospital discharge, whichever is first.

Every attempt should be made to perform follow-up visits in person. Should extenuating circumstances (e.g., COVID-19 global pandemic travel restrictions) impact a site's ability to perform follow-up visits in person, notify the sponsor and make every attempt to collect the protocol required data via other means (e.g., telephone, video conference, blood and urine labs at a non-hospital lab).

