For this clinical study, adverse events will be collected post informed consent when invasive or non-standard-of-care screening begins (i.e. imaging or invasive hemodynamics). For safety reporting, all adverse events will be reported until the patient exits the study. Any unresolved procedural or device related adverse events that are still ongoing past study exit will be reported as being unresolved or unresolvable.

Enrollment will pause if any of the following serious, procedure related adverse events occur:

- Death (Aortix procedure related only)
- Aortic Injury Requiring Surgical Intervention to Repair (Aortix procedure related only)

Enrollment will be paused until the event can be evaluated and discussed with regulatory agencies if appropriate and approval is granted to continue enrollment.

For purposes of this study, minor clinical changes which would normally occur for this patient during the course of having heart failure which are not related to the device, the procedure or the therapy, need not be reported. Examples include but are not limited to ongoing poor appetite, weakness or fatigue. Investigator discretion is expected. If unsure, report as an adverse event.

It is anticipated that due to underlying baseline conditions, all laboratory values may not remain in the range of normal for a given participant. Investigator discretion is required to determine if a laboratory value that remains out of range is associated with an untoward clinical finding that should be reported as an adverse event.

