7.8 Main Study Endpoints

7.8.1 Primary Safety

A Primary Safety analysis will be performed for the As-Treated population to include:

- Percentage of patients with Serious Adverse Events (SAE) defined as the total number of patients with a CEC-classified SAE from the time of enrollment through 30 days post-implant Follow-Up, compared to the total number of patients within the population. Patients with two or more CEC-classified SAE will be counted only once.
- Percentage of patients with Serious Procedure Related Adverse Events (SPRAE) defined as the total number of patients with CEC-classified SPRAE from the time of implant procedure through 30 days post-implant Follow-Up, compared to the total number of patients within the population. Patients with two or more CEC-classified SPRAE will be counted only once. Procedure Related Adverse Events will be defined as any AE related to Aortix Pump Deployment Procedure or Aortix Pump Retrieval Procedure.

Descriptive summaries will be provided for both Percentage of patients with SAE and Percentage of patients with SPRAE for As-Treated population. Corresponding listing will be provided for As-Treated Population.

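### The protocol lets a patient be withdrawn after a non-fatal terminal event, which ends adverse-event reporting before the 30-day visit, and the SAP has no rule for the missing follow-up

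*Protocol*

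**What the plan says.** **Withdrawal.** Protocol Section 3.6: "A patient may also be withdrawn if they have a terminal event". It lists these events as death, dialysis, CRRT, ultrafiltration, LVAD implantation, and transplant of heart or kidney. The wording is permissive. The same section opens with a commitment to try to keep all patients in the study.

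**End of adverse-event reporting.** Protocol Section 6: "For safety reporting, all adverse events will be reported until the patient exits the study". Procedure- or device-related events still open at exit are kept and reported as unresolved. Events that begin after exit have no route into the data.

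**Planned follow-up.** Protocol Section 4.8: "Patients with the pump implanted will be followed for adverse events for 30 days" (± 7 days) after device retrieval. In that section a terminal event has one function: it closes the extra follow-up of patients who are still in hospital at day 30 because of a device- or procedure-related event.

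**Endpoints and denominators.** The primary safety and device-related endpoints run to the 30-day visit (Protocol Sections 3.3.1 and 3.3.2; SAP Sections 5.1 and 5.2). SAP Section 7.8.1 counts each As-Treated patient with a CEC-classified event once, "compared to the total number of patients within the population". SAP Section 7.8.2 does the same for device-related events, over the ITT or As-Treated population. Neither section says how to treat a patient who leaves before day 30.

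**The concern.** Leaving the study can depend on how the patient is doing. The trigger is a bad cardiac or renal outcome. Appendix C already assigns AKIN stage 3, the highest stage it lists, to anyone on renal replacement therapy. Patients who leave this way are therefore unlikely to resemble those who stay, although calling them the highest-risk patients is an inference and not something the documents state.

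Once such a patient leaves, a later access-site, retrieval-related or device-related event is not collected, yet the patient stays in the denominator. The 30-day percentage then reads as if the whole population had been observed to day 30. The study has at most 30 implanted patients and is meant to give initial safety data and inform later studies, so a few patients scored this way could visibly move a primary safety figure.

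**Working it through.** The plan states no figure on this point, so there is none to reproduce. The check has two parts: reading the sections together, then bounding the effect.

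**1. Do the sections conflict?** Take an implanted patient who starts CRRT before the 30-day visit.
- Under Section 4.8 alone, adverse-event follow-up continues to 30 days after retrieval. The terminal-event clause does not apply, because it concerns only the extension beyond day 30.
- Under Section 3.6 with Section 6, the investigator may withdraw the patient, and adverse-event reporting then stops.

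Both courses comply with the text, so sites can differ.

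**2. Do the safeguards cover this patient?**
- Encouragement to keep attending visits (Section 3.6) applies when the patient asks to withdraw.
- Modified follow-up by telephone or records (Section 3.6) is for a patient who is considering withdrawal.
- Removal by the investigator requires only a documented reason and date (Section 3.6).
- Vital status at study closure (Section 3.6) captures death but not adverse events. Section 4.10 requires death reports only for deaths before exit.

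None of these keeps adverse-event collection going after withdrawal for a terminal event.

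**3. How is the patient scored?** SAP Section 3.2 bases percentages on non-missing values unless otherwise specified. Section 7.8.1 does specify otherwise, by naming the whole population. A patient with no counted event on record is in the denominator and not in the numerator.

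**4. How large could the effect be?** Inputs:
- N = 30 As-Treated patients, the planned maximum (Protocol Section 7, SAP Section 2.3).
- x = patients with an observed counted event; x = 6 is used as an example.
- k = patients withdrawn before day 30 with no earlier counted event. The documents give no terminal-event rate, so k = 1, 3 and 6 are assumptions.

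Reported percentage = 100x/N. Worst case = 100(x + k)/N. Maximum understatement = 100k/N, whatever the value of x.

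| k | Reported (x = 6) | Worst case | Maximum understatement |
|---|---|---|---|
| 1 | 6/30 = 20.0% | 7/30 = 23.3% | 1/30 = 3.3 points |
| 3 | 6/30 = 20.0% | 9/30 = 30.0% | 3/30 = 10.0 points |
| 6 | 6/30 = 20.0% | 12/30 = 40.0% | 6/30 = 20.0 points |

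The worst case assumes that every such patient has an uncounted event. If each instead has probability q of a first counted event after exit, the expected understatement is 100kq/N. With q between 0.1 and 0.5 (again an assumption):
- k = 1: 0.33 to 1.67 points
- k = 3: 1.0 to 5.0 points
- k = 6: 2.0 to 10.0 points

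Where the ITT population is the denominator and exceeds 30, the effect per patient is slightly smaller.

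**5. Which endpoints are exposed?** Each patient counts once. A terminal event may itself be adjudicated as an SAE, which puts the patient in the any-SAE numerator before exit, so k is smaller for that endpoint. The serious procedure-related and device-related percentages lack this protection.

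**The case against.** The strongest reply is that the default is full follow-up. Section 3.6 says that a patient may be withdrawn, not must be, and asks for every effort at retention; Section 4.8 is unconditional. This stands. A reader might infer that safety follow-up is cut short, or that the reported rates are biased. The documents support only that early exit is permitted and that bias can follow from it.

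A reader might also infer that all the terminal events are expected in this population. The text does not support that. Exclusion 11 removes patients with a heart transplant planned before the 30-day visit, and Section 1.1 says that temporary or permanent mechanical support is rarely considered (under 2%). Renal replacement and ultrafiltration are the plausible cases, and the protocol plans to report their use: "Utilization of continuous renal replacement therapy (CRRT), ultrafiltration and dialysis".

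It is tempting to express the loss as patient-days. That needs a terminal-event rate and a time of onset, and the documents give neither. It also would not show how far a percentage of patients moves.

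Lastly, SAP Section 7.1 already reports premature discontinuations with reasons, and Section 5.4 covers CRRT, ultrafiltration and dialysis. A careful reader could trace early withdrawals from these outputs. They leave the primary safety percentages as computed, however, and do not show who lacks complete 30-day safety follow-up.

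The study is also a feasibility study with no safety threshold and with patient-by-patient review. That limits the consequence without removing the inconsistency.

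**Conclusion.** The point holds as a conflict between sections that permits outcome-dependent loss of safety data, combined with an SAP that has no rule for that loss. The possible bias in the serious procedure-related and device-related percentages is downward. Its ceiling is 3.3 percentage points per affected patient with 30 As-Treated patients: up to 3.3, 10 or 20 points for 1, 3 or 6 patients.

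These are bounds, not estimates. They assume 30 As-Treated patients, that the investigator uses the option to withdraw, that exit comes before the 30-day visit, and that no event of the same type was counted earlier. The any-SAE percentage is less affected, and deaths are partly protected by the vital-status request. The change should be made because it is cheap; nothing here shows that the safety results will be wrong.

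**What to change.** **Protocol.** Reconcile Sections 3.6, 4.8 and 6. State that a non-fatal terminal event does not end adverse-event and vital-status follow-up before the 30-day visit unless the patient withdraws consent. Extend the telephone, treating-physician and records contact in Section 3.6 to these patients. This concerns data collection only and changes no treatment.

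**SAP.** In Section 7.1, next to the existing discontinuation and renal-replacement reporting, add the number of patients without complete 30-day safety follow-up, with reasons and a listing. In Sections 7.8.1 and 7.8.2, give a best-case and a worst-case value for the serious procedure-related and device-related percentages, with those patients counted first as event-free and then as having an event.

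**Cost.** A short wording change, one added disposition line with its listing, two extra rows per affected table, and a few extra safety contacts.

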4.10 Subject Death

If a patient dies during or after deployment of the Aortix Pump, the Investigator will make every effort to have an autopsy performed to help determine the extent to which the patient's death was related to the device/procedure. The Aortix pump should be returned to Procyron.

All subject deaths which occur in subjects prior to study exit/withdrawal, regardless of causality or study relationship, must be reported to Procyron. Investigator must provide a detailed narrative summary to include as much detail that is known regarding the circumstances surrounding the death. All deaths will be brought to the clinical event committee for adjudication and will be reported using standard mortality classifications.

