7.12 Deaths

The number of patients who died during the study will be provided along with a vignette discussing the primary cause of death, the temporal course of death and classification for As-Treated population by subgroup and overall.

Only CEC classification of Deaths will be used for analysis.

Listing with detailed information will be provided for the ITT population.

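### A death by day 30 in a patient withdrawn early can be left out of the death table and the SAE rate, because the dated vital status the protocol seeks enters no analysis

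*Protocol*

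**What the plan says.** **Vital status.** Protocol 3.6 has investigators asked, at study closure, whether each patient is alive and, if not, when death occurred. The sources are public and local regulations apply. It adds: "Knowledge of the vital status at study closure in all patients is crucial for the integrity of the study".

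**Where reporting stops.** For deaths, Protocol 4.10 says: "All subject deaths which occur in subjects prior to study exit/withdrawal, regardless of causality or study relationship, must be reported". For adverse events, Protocol Section 6 says that "all adverse events will be reported until the patient exits the study". After voluntary withdrawal, Protocol 3.6 provides that "all data collected from the time of informed consent to the time of voluntary withdrawal may be used".

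**How a patient can leave early.** Protocol 3.6 allows voluntary withdrawal. It also allows withdrawal after a terminal event, and several of these are not fatal: dialysis, ultrafiltration, CRRT, LVAD implant, and heart or kidney transplant.

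**Follow-up window.** Protocol 4.8: "Patients with the pump implanted will be followed for adverse events for 30 days (± 7 days) post device retrieval". The protocol's SAE endpoint (3.3.1) carries the "timeframe: enrollment to 30 day visit", and SAP 5.1 repeats this. SAP 7.8.1, however, words the end of the window as a 30-day follow-up counted from implant.

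**Counting.** SAP 7.8.1 divides the number of patients with a CEC-classified event by all As-Treated patients, each counted once. SAP 7.12 says: "The number of patients who died during the study will be provided along with a vignette". It restricts the analysis to CEC-classified deaths and does not say when the study ends for an individual patient.

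**The concern.** The numerator and the denominator of the safety percentages follow different rules. An implanted patient stays in the denominator whatever happens next, but can enter the numerator only through an event that was reported and then classified by the CEC. Once a patient is withdrawn, the stated duty to report a death ends. The SAP has no rule for incomplete follow-up, no censoring and no time-to-event estimate, so unobserved time counts as event-free time.

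Death is an SAE by definition (Protocol 6.2), and the protocol already plans to obtain the date of death. A death could therefore be known to the sponsor, fall within 30 days, and still have no stated route into either safety result. In a study of about 30 treated patients, meant to show initial safety and inform later trials, one such death is visible in the reported rate.

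**Working it through.** No formula in the plan produces a safety rate that could be reproduced. The check therefore sets the rules side by side and then sizes the effect.

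**1. The path of one patient.** Take an implanted patient who withdraws, or is withdrawn after a non-fatal terminal event, before day 30 and then dies by day 30.

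| Step | Rule | Result |
|---|---|---|
| Must the death be reported? | Protocol 4.10: deaths before exit or withdrawal | No stated duty |
| Is it collected as an adverse event? | Protocol Section 6: until exit | Not after exit |
| Is the date sought? | Protocol 3.6: closure check | Yes |
| Does the SAP use that date? | Vital status is not mentioned | No |
| Is the patient in the denominator? | SAP 7.8.1: all As-Treated patients | Yes |
| Is the patient in the death table? | SAP 7.12: CEC-classified deaths, study period undefined | Not assured |

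The general SAP rule that percentages use non-missing values (3.2) does not help, because 7.8.1 specifies its own denominator.

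**2. Which results move.** The death count is affected in every such case. The SAE percentage is affected only if the patient had no earlier counted SAE; someone withdrawn after starting CRRT, for example, may well already be counted. The procedure-related percentage is affected only if the CEC would class the death as procedure-related.

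**3. Size.** The planned number of implanted patients is 30 (SAP 2.3). With k uncounted patients the shortfall is k/30, so one patient is 1/30 = 3.3 points.

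A worst-case bound for the SAE rate with x patients counted and w early exits without a counted event is (x + w)/30. The documents give neither x nor w, so these values are assumed:

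| x | Reported | w = 1 | w = 2 | w = 3 | w = 5 |
|---|---|---|---|---|---|
| 0 | 0.0% | 3.3% | 6.7% | 10.0% | 16.7% |
| 3 | 10.0% | 13.3% | 16.7% | 20.0% | 26.7% |

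**4. The visit window.** An in-window visit falls between 30 − 7 = day 23 and 30 + 7 = day 37 after retrieval. With t days of therapy, that is day t + 23 to day t + 37 after implant. Two durations serve as illustrations: 2 days (the initial minimum in Protocol 4.5.2.1) and 7 days (the tested duration in 4.5).

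- t = 2: visit on day 25 to 39 after implant. The earliest visit is 30 − 25 = 5 days short of day 30 after implant.
- t = 7: visit on day 30 to 44 after implant. The shortfall is 0 days.

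Day 30 after retrieval is day t + 30 after implant. A literal post-implant horizon therefore stops t days before the protocol's nominal one: 2 and 7 days in these examples. SAP 7.14, which lists changes from the protocol, does not mention this.

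**The case against.** The strongest reply is that the gap is narrow.

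- **Loss to follow-up.** A reader might infer that a patient lost on day 5 who dies on day 12 goes uncounted. The documents do not support that. No visit is scheduled between 72 hours or discharge and the 30-day visit (Appendix A). Loss is declared only after three calls, a letter if the calls fail, and contact with the family doctor, if known, about survival and adverse events (Protocol 3.6). The day-12 death would normally precede exit, so it must be reported, and Protocol 4.10 sends deaths to the CEC.
- **Early visits.** A reader might infer that an event after a day-23 visit is miscounted. It is not: the endpoint runs to the 30-day visit, so that event lies outside it by definition. This is unequal follow-up, and it misleads only if the result is read as a fixed day-30 risk.
- **Direction.** A reader might infer that the window biases the rate in the device's favour. Assume a constant hazard and a 20% risk at day 30. A day-23 visit then captures 1 − 0.80^(23/30) = 15.7% and a day-37 visit 1 − 0.80^(37/30) = 24.1%, which average 19.9%. Visits spread evenly around day 30 nearly cancel. The documents also give no evidence on whether patients who withdraw are sicker.
- **Mitigations.** Withdrawn patients with a pump are encouraged to continue visits, and anyone considering withdrawal must be told of telephone, relative, physician or records follow-up (Protocol 3.6). The study is descriptive, and no hypothesis test rests on these rates.

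All of this stands, and it confines the problem to death after early withdrawal. It does not remove it, because none of these provisions is a counting rule. The CEC sentence in 4.10 follows a duty limited to deaths before exit or withdrawal, and nothing says that a death found only at the closure check goes to the CEC.

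**Conclusion.** The point holds for patients withdrawn before day 30 who then die by day 30. Under the plan as written, such a death can be absent from the death table and, if no earlier SAE was counted, the patient can be counted as event-free. Each case is 3.3 points of 30. This rests on 30 implanted patients and on reading the reporting duties literally; the number of cases cannot be estimated because no withdrawal or mortality rate is given.

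Two lesser matters accompany it. The ± 7 day window gives unequal follow-up. The SAP's implant-based wording also conflicts with the protocol's retrieval-based follow-up, although it could be a loose name for the same visit.

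A reader might also infer that SAP 7.12 takes in every death up to study closure, mixing long follow-up for early patients with short follow-up for late ones. That is only one possible reading of an undefined phrase, and the SAP does not commit to it. Finally, vital status can recover deaths but not non-fatal events.

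**What to change.** In SAP 7.8.1 and 7.12:

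1. Reconcile the implant and retrieval anchors with the protocol and state one day-30 horizon.
2. Count every death dated on or before that day in the SAE rate and the death table, whatever its source. Include deaths after withdrawal and those found at the closure check, subject to consent and local regulations, and send them to the CEC.
3. Report the number of patients with unknown vital status at day 30 and the number without complete adverse event follow-up to day 30. Give a worst-case bound for the SAE rate.
4. List later deaths separately, with follow-up time.
5. Keep SAEs observed up to the 30-day visit in the protocol-defined endpoint. Show those with onset after day 30 separately rather than dropping them.

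The cost is SAP wording, a little extra analysis, some added CEC work where public records are thin, and possibly a slightly higher reported event rate. The vital-status check is already planned, and nothing in treatment changes.
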